4.2.3 Exploratory objective

Patients who step down their prescribed dose of non-extra fine beclomethasone dipropionate with Volumatic[®] and Aerochamber[®] will be compared in terms of baseline exacerbation rate and SABA usage.

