5.2 Study design (questionnaire outcomes)

A longitudinal study to compare patient-reported side effects for asthma patients prescribed non extra fine beclomethasone with Volumatic[®] spacer or Aerochamber[®] spacer (Figure 4). The index date of the study is the date of administration of the BLF Questionnaire. This study design will also be used to explore patients who step down at the index date with Volumatic and Aerochamber spacers. This exploratory objective will explore the baseline year (ie: year before index) in terms of comparative efficacy. If required (due to insufficient patients) an additional study design will be incorporated which will consider date of step down as index date (instead of date of BLF questionnaire).

[figure not shown]

Figure 4: Study Design (questionnaire outcomes)

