7.1 Demographic and baseline variables for patient questionnaire outcomes

- Gender (male/female)

- Age of patient (years, at index date)
- Body Mass Index (BMI, at time nearest index date, calculated from height and weight data if available, otherwise taken from practice-recorded BMI value, detailed definition in Appendix 1)
- Smoking status (identified by Read code, closest to index date)
- SABA daily dose calculated 1 year prior to index date*
- Percentage predicted peak flow (closest to index date)
- Total cumulative ICS dose
- Spacer type
- Total cumulative non-extrafine beclomethasone dipropionate therapy
- Duration of ICS therapy
- Number of exacerbations (ATS/ERS 2015 consensus definition[†]) from 1 year prior to index date
- Number of oral corticosteroid prescriptions from 1 year prior to index date
- Number of antibiotic prescriptions for lower respiratory tract infections from 1 year prior to index date
- History of comorbidities related to asthma:
 - Pneumonia (Read code diagnosis from 1 year prior to the index date)
 - Diabetes (Read code diagnosis and/or antidiabetic drugs ever prior to the index date)
 - Ischaemic heart disease (Read code diagnosis before one year prior to the index date)
 - Rhinitis (Read code diagnosis, including chronic and allergic rhinitis and prescriptions for nasal steroids between one year prior to index date)
 - Eczema (Read code diagnosis between one year prior to index date)
 - Osteoporosis (Read code diagnosis between one year prior to the index date)
 - Charlson Comorbidity Index (based on Read code diagnoses between one year prior to index date, detailed definition in Appendix 1)

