7.5 Step down outcomes

- 1) Number of severe exacerbations in baseline year
- 2) Daily average SABA category in baseline year

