8.3 Matching

Initially, baseline data will be compared between unmatched cohorts. Exact matching for categorical variables and coarsened exact matching for numeric variables will be used to match patients using 1:1 nearest neighbour matching, without replacement. Matching variables such as demographic data, disease co-morbidity and indicators of disease severity will be considered for selection using a combination of baseline data analysis and predictive modelling of the baseline data in relation to the primary outcome variable (independently of treatment group).

If patient numbers allow, patients will be matched on sub groups for age (under 16s and 16-65 year olds) and high/low average ICS dose (1000 µg non-extrafine beclomethasone dipropionate or more/under 1000 µg non-extrafine beclomethasone dipropionate). For the sub-question of step down patients, matching will be implemented if the numbers are sufficient.

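### Section 8.3 leaves step-down patients open to being matched on baseline-year exacerbations, SABA use or their components, which are the outcomes of that comparison

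*Protocol*

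**What the plan says.** **Outcomes.** Protocol 4.2.3 states that step-down patients on the two spacers "will be compared in terms of baseline exacerbation rate and SABA usage". Section 7.5 lists two outcomes: "Number of severe exacerbations in baseline year" and "Daily average SABA category in baseline year". Section 5.2 fixes the window: "This exploratory objective will explore the baseline year (ie: year before index) in terms of comparative efficacy". Section 8.4.2 applies a Wilcoxon test to the baseline-year exacerbation rate and daily SABA dosage of patients who step down at index.

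**Matching.** Section 8.3 describes one procedure: exact or coarsened exact matching, 1:1, without replacement. On its inputs it says "Matching variables such as demographic data, disease co-morbidity and indicators of disease severity will be considered for selection". Selection combines analysis of the baseline data with modelling of what predicts the primary outcome. The section then extends matching to this question: "For the sub-question of step down patients, matching will be implemented if the numbers are sufficient". It gives no separate variable set and no exclusion for it.

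**Baseline variables.** Section 7.1 lists "SABA daily dose calculated 1 year prior to index date", and also exacerbations, oral corticosteroid prescriptions and antibiotic prescriptions for lower respiratory tract infection, all over the year before index.

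**The concern.** Matching on baseline severity is normally sound because the outcome comes later. Here it does not: the baseline year is the outcome year. A severity indicator taken from that year may be the quantity under comparison, or a part of it, and matching on it makes the spacer groups alike on the result.

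Section 4.1 asks whether Aerochamber patients have greater efficacy that leads to a lower daily dose. If matching used these variables, a real difference could shrink or vanish, and the resulting null could be reported as equal efficacy of the two spacers.

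**Working it through.** **Step 1: overlap of outcomes and candidate variables.**

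| 7.1 variable, year before index | Relation to the step-down outcomes |
|---|---|
| Exacerbations | Outcome (4.2.3, 7.5, 8.4.2) |
| SABA daily dose | Outcome (4.2.3, 7.5, 8.4.2) |
| Oral corticosteroid prescriptions | An acute course counts as an exacerbation (15.1.2) |
| Antibiotics for lower respiratory infection | Antibiotics with a lower respiratory consultation count as an exacerbation (15.1.2) |

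**Step 2: does the selection rule keep them out?** Neither part of it asks whether a variable is a step-down outcome. Section 8.3 begins by comparing baseline data between the unmatched spacer cohorts. If the spacers truly differed in exacerbations or SABA use, that comparison would tend to flag exactly these variables.

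**Step 3: the limiting case.** If both members of every pair have the same exacerbation count y, each pair contributes y − y = 0. The matched mean difference is then zero whatever the difference before matching. With categories such as 0, 1 and 2+, a difference can survive only inside the open-ended category.

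**Step 4: the plan's own figure.** The protocol gives no figure for the step-down analysis. Its only sample size, 293 and 147 in 8.1, belongs to the primary comparison and reproduces:

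- SE = √(0.21/147 + 0.21/293) = √(0.001429 + 0.000717) = 0.0463
- 0.13/0.0463 − 1.960 = 0.85, which gives 80.1% power against the stated 80%

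The present point does not depend on it.

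**Step 5: illustrative simulation.** Every input is an assumption. There were 293 patients per spacer and 500 replicates. Exacerbation counts were gamma-Poisson with shape 1 and means of 0.8 and 0.5 per year, a true difference of 0.30. SABA dose was log-normal, correlated with exacerbation risk, with a true ratio of √(0.8/0.5) = 1.26. An oral steroid course accompanied 80% of exacerbations. Matching was 1:1 within four age bands plus the variable shown, followed by a rank-sum test at 0.05.

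| Matched on age band and | Mean pairs | Exacerbation difference | Rejected | SABA median ratio | Rejected |
|---|---|---|---|---|---|
| nothing further | 276 | 0.303 | 88% | 1.28 | 96% |
| SABA category | 247 | 0.240 | 61% | 1.02 | 0% |
| steroid courses (0, 1, 2+) | 253 | 0.059 | 0% | 1.23 | 83% |
| exacerbations (0, 1, 2+) | 251 | 0.038 | 0% | 1.22 | 79% |
| exacerbations and SABA category | 225 | 0.033 | 0% | 1.02 | 0% |

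The share of the exacerbation difference that remains is 0.038/0.303 = 13% after matching on the outcome in categories, 0.059/0.303 = 19% after matching on a component, and 0.240/0.303 = 79% after matching on a correlate. The fall in rejections is not mainly lost sample size: 251 pairs remain, against 276.

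**The case against.** The protocol does not say that step-down patients will be matched on these variables. It says that classes of variable will be considered, names none, and ties selection partly to the primary outcome of thrush or hoarseness. Section 7.1 labels nothing a severity indicator. Percentage predicted peak flow, cumulative ICS dose and ICS duration would also qualify, and they are neither outcomes nor components of them. Section 7.5 refers to severe exacerbations, which 15.1.2 does not define separately, so antibiotics are a proven component only of the exacerbation rate in 4.2.3 and 8.4.2. Matching depends on numbers, 5.2 itself anticipates too few step-down patients, and the comparison may end up unmatched. A variable list for an exploratory analysis may also sit in an analysis plan that is not at hand.

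Most of this stands, and it limits the point to what 8.3 permits. A reader might go further in three ways that the protocol does not support:

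- *That the matched result is null whatever the truth.* This holds only for matching on an outcome or a near-duplicate. In the table, matching on one outcome leaves most of the difference in the other.
- *That the primary matched pairs will be reused.* No section says so.
- *That severity measured 13 to 24 months before index is a safe substitute.* Section 6.1 requires the spacer prescription only at some time before the questionnaire, so that window may already follow spacer start. Under the 5.2 fallback, with step-down as the index date, the data may not reach back that far.

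The point about the analysis plan does not dispose of the matter. The protocol itself fixes both the baseline-year outcomes and a baseline-severity matching procedure extended to the same patients.

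**Conclusion.** The concern holds as a gap in 8.3: if numbers permit matching, the stated procedure can condition the step-down comparison on its own outcomes. The direction is general. Matching on an outcome or near-duplicate removes most or all of the spacer difference in it, and matching on a correlate removes part.

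The size is illustrative. It rests on assumed rates, dispersion, correlation and steroid share, and on 293 patients per spacer, a number taken from the whole primary comparison of which step-down patients are only a part. The primary and secondary conclusions are unaffected. What is at risk is an exploratory null being read as equal efficacy.

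**What to change.** In 8.3, state that for the step-down comparison:

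- exacerbations, SABA use, oral steroid courses and antibiotics for lower respiratory infection from the year before index are not matching variables;
- any pairs matched on them are not used for this comparison;
- matching uses demographics, comorbidity and other characteristics that are neither outcomes nor their components;
- severity indicators from before the outcome year may be used only where they precede the first spacer prescription and the data are available.

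This takes a few lines of text and no new data. The downside is weaker control of confounding by severity. That is tolerable in an exploratory comparison and should be stated when the result is reported.

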8.4 Analysis of study outcomes

8.4.1 Primary analysis: Questionnaire based adverse events

Adverse events as total and individual events in the questionnaires will be compared using a conditional Poisson regression model. The model will use empirical standard errors and adjustments will be made for potential baseline confounders.

The adjusted rate ratio with 95% confidence interval will be reported.

Non-inferiority in patient reported adverse events (oral thrush OR hoarseness) will be achieved if the proportion of Clenil/Aerochamber is no more than 13% higher (based on the upper boundary of the 95% confidence interval) than the proportion of patients on Clenil/Volumatic.¹⁴

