8.0 Statistical analysis

8.1 Software used and power calculation

The dataset will be analysed using SPSS version 23, SAS version 9.3, Stata SE version 14 (StataCorp, College Station, TX) and Microsoft Office EXCEL 2013, as appropriate.

The study was powered using the occurrence of oral thrush as the representative adverse event. The occurrence of adverse events is 34% based on the oropharyngeal side effects in users of ICS in a real life setting reported in the literature¹³.

The minimum study numbers are based on the following assumption:

When the sample sizes in the groups are 293 and 147, a two-group large-sample normal approximation test of proportions with a one-sided 0.025 significance level will have 80% power to reject the null hypothesis that the test and the standard are not equivalent (the difference in proportions, $p_T - p_S$, is 0.130 or farther from zero in the same direction) in favor of the alternative hypothesis that the proportions in the two groups are equivalent, assuming that the expected difference in proportions is 0.000 and the proportion in the standard group is 0.300.

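### The 13% non-inferiority margin was set as a difference in proportions, but the only interval section 8.4.1 names is for a rate ratio, and the model it names does not list the composite endpoint

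*Protocol*

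**What the plan says.** Three statements in the Protocol bear on the primary decision.

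- **Sample size (section 8.1).** The calculation concerns a difference in proportions, test minus standard. The null hypothesis is that this difference "is 0.130 or farther from zero in the same direction". The other inputs are "When the sample sizes in the groups are 293 and 147" and "assuming that the expected difference in proportions is 0.000 and the proportion in the standard group is 0.300", with 80% power at one-sided 0.025.
- **Primary model (section 8.4.1).** "Adverse events as total and individual events in the questionnaires will be compared using a conditional Poisson regression model". The section then says: "The adjusted rate ratio with 95% confidence interval will be reported". No other effect measure or interval is named there.
- **Decision rule (section 8.4.1).** Non-inferiority on the composite of oral thrush or hoarseness is achieved "if the proportion of Clenil/Aerochamber is no more than 13% higher (based on the upper boundary of the 95% confidence interval", relative to the Volumatic proportion. The rule does not say whether 13% means percentage points or a relative increase, or which interval supplies the upper boundary.

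Section 4.2.1 names the same composite as the primary objective. Section 7.3 lists six questionnaire items, to be analysed in total and individually, without the composite. The mock primary tables in section 15.2.1 have rows for the total and the six items only, and a confidence interval column with no scale.

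**The concern.** The margin and the planned estimate are on different scales. A conditional Poisson model works on the log scale and yields a ratio. The margin is a difference, and nothing in the Protocol turns one into the other. A reader who follows section 8.4.1 in order has one 95% interval to hand, for a ratio, and would naturally hold its upper limit against 1.13. That is a much stricter test than the one the study was sized for.

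The endpoint adds to the gap. The rule concerns a yes/no composite of two items, while the model sentence covers the six-item total and each item separately. The quantity that decides the study is therefore neither on the scale of the named interval nor among the variables named for the model. If this is settled only after results are seen, the choice of scale can decide the conclusion.

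**Working it through.** **Inputs.** From section 8.1: sizes 293 and 147, proportion 0.300 in both groups, margin 0.130, one-sided 0.025. Section 8.1 also cites a 34% event rate, used below as a sensitivity value. The groups are treated as independent and unadjusted, because the Protocol gives no within-pair correlation.

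**1. Reproduce the Protocol's figure on the difference scale.**

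SE(difference) = √[p(1−p)(1/n₁ + 1/n₂)] = √[0.30 × 0.70 × (1/293 + 1/147)] = 0.0463

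Power = Φ(0.13/0.0463 − 1.96) = 80.1%

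Solving for size at 2:1 also returns 293 and 147. The stated figures therefore follow from an absolute margin of 0.130.

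**2. Put the two readings of 13% side by side.**

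| Volumatic proportion | +13 points allows up to | as a ratio | ratio 1.13 allows up to | as a difference |
|---|---|---|---|---|
| 0.30 | 0.43 | 1.43 | 0.339 | +3.9 points |
| 0.34 | 0.47 | 1.38 | 0.384 | +4.4 points |

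**3. Apply both to one data set.** Take nearly identical rates at the planned sizes: 88/293 (0.3003) for Aerochamber and 44/147 (0.2993) for Volumatic.

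- Difference: +0.1 points. SE = √[0.3003 × 0.6997/293 + 0.2993 × 0.7007/147] = 0.0463. The 95% CI is −9.0 to +9.2 points. The upper limit is below 13, so non-inferior.
- Ratio: 1.003. SE(log ratio) = √[0.6997/88 + 0.7007/44] = 0.1545. The 95% CI is 0.74 to 1.36. The upper limit is above 1.13, so not non-inferior.

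Section 8.1 does not say which spacer has the larger group. With the groups swapped, the upper limits are +9.0 points and 1.35, and the two readings disagree in the same way.

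**4. Check whether converting the margin to a ratio would be enough.** At p = 0.30, SE(log ratio) = √[(0.7/0.3)(1/293 + 1/147)] = 0.1544. Against 1.43, power = Φ(ln 1.4333/0.1544 − 1.96) = Φ(0.37) = 64.5%. Converting the margin at the planning rate does not reproduce the test that was sized. It also corresponds to 13 points only if the Volumatic rate is in fact 30%.

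**The case against.** The strongest reply is that the Protocol does settle the margin. Section 8.1 defines it as a difference in proportions, section 8.4.1 compares one proportion with another, and the number is the same. No section states a ratio margin. The rate-ratio sentence and the non-inferiority rule are also separate paragraphs, and the rule does not say that its interval is the ratio interval. On this view only the method for the difference interval is missing, and a statistical analysis plan could supply it.

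Most of that stands. The intended margin is 13 percentage points, and the point should not be presented as an open choice between two equally supported margins. What does not stand is that only detail is missing. The Protocol already fixes a model, an effect measure and a rule, and these do not fit together. A later document would have to change or add to the primary analysis.

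A reader might go further and infer that the study is grossly underpowered. Against a ratio of 1.13, power at 293/147 is Φ(ln 1.13/0.1544 − 1.96) = 12%, and about 2,450 per group would be needed for 80%. The documents do not support that as a finding, because both figures belong to a margin that no section states.

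The missing composite row in the mock tables is editorial by itself. It matters only because the model sentence omits the composite too.

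**Conclusion.** The point holds as a scale mismatch in the primary decision rule with a known intended margin. Sections 8.1 and 8.4.1 must be brought into line before the outcome data are analysed. As written, no named analysis yields an interval for the difference in the composite. Applied literally to the one interval that is named, the rule shrinks the allowed excess from 13 points to about 3.9 points at a 30% rate (4.4 at 34%), so data that meet the intended margin can fail.

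The worked example rests on independent groups, large-sample intervals, no covariate adjustment and exactly the planned sizes. Matching and adjustment would change the interval widths, but they would not put the margin and the estimate on the same scale.

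Section 8.3 plans 1:1 matching while section 8.1 assumes 2:1 groups. Any loss of power from that is a separate matter and is not counted here.

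**What to change.** In section 8.4.1:

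- State the margin as 13 percentage points, absolute, to agree with section 8.1.
- Define the primary endpoint as a binary variable per patient: oral thrush or hoarseness, yes or no.
- Make the primary estimate the adjusted risk difference, Aerochamber minus Volumatic, in the matched set, with a two-sided 95% interval that respects the matching. Two workable routes are an identity-link model with matched-pair robust standard errors, or standardisation from an unconditional Poisson or logistic model with a bootstrap that resamples pairs. Standardising from the purely conditional Poisson model does not work directly, because conditioning on the pair removes the baseline risk that a difference needs.
- Claim non-inferiority if the upper limit is below +0.13.
- Keep the adjusted rate ratio as a supportive result.

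Adding a composite row to the mock primary tables and naming the scale of the interval column would follow as an editorial change. If the sponsor prefers to decide on a ratio, the ratio margin would need its own justification and section 8.1 would need to be recalculated.

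The cost is revised wording and one additional model output. No new data are needed.

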8.4.2 Secondary analysis – database outcomes

The total number of adverse events as listed in the Summary of Product characteristics in the outcome period will be compared between treatment groups compared using a conditional

Poisson regression model. The model will use empirical standard errors and adjustments will be made for potential baseline confounders.

The adjusted rate ratio with 95% confidence interval will be reported.

Exploratory analysis – The exacerbation rate and separately the daily SABA dosage for patients during the baseline year who step down ICS at the index date treated with an Aerochamber spacer will be compared to patients prescribed a Volumatic spacer and compared with a Wilcoxon ranked test.

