3.0 Background

Asthma is considered a heterogeneous obstructive lung disease caused by an inappropriate inflammatory reaction in the airways. Increased mucus production and bronchospasm can lead to exacerbations and significant mortality. Narrowed airways can result in reduced quality of everyday living – the Royal College of Physicians three questions surveys whether asthma is controlled by asking the patient whether they have nocturnal disturbances, whether asthma limits activity, and whether they suffer from any daytime symptoms. Treatment of asthma is centered around the use of inhaled corticosteroids, which are recommended in all but the mildest patients with asthma¹. The latest GINA guidelines recommend patients who require their reliever more than once a fortnight be prescribed inhaled corticosteroids¹. Reducing the inflammatory response not only helps control the disease, prevents exacerbations and reduces the daily symptoms, but also might help to reduce any chronic changes that occur as a result of long term inflammation.

However, the use of corticosteroids can cause significant side effects, especially when prescribed to young children or when higher doses are required. Inhaled corticosteroids are dispensed at significantly lower doses than oral corticosteroids, significantly reducing the risk of glucocorticoid side effects compared to oral therapy ²(Table 1).

System Class	Adverse Reaction	Frequency
Infections	Oral thrush	Very common
Immune system	Rash, urticarial, pruritus, erythema	Uncommon
	Oedema	Very Rare
Endocrine	Adrenal suppression, bone density reduction, growth retardation	Very Rare
Psychiatric disorders	Psychomotor hyperactivity, sleep disorder, depression, anxiety, behavioural disorders	Unknown
Nervous system disorders	Headache	Unknown
Eye disorders	Cataracts, glaucoma	Very Rare
Thoracic disorders	Hoarseness, throat irritation	Common
	Cough, bronchospasm, wheezing, dyspnoea	Very rare
Gastrointestinal	Nausea	Unknown

Table 1: Side effects of non-extrafine beclomethasone dipropionate listed by system ³

Unlike oral therapy, the use of inhaled corticosteroids requires a meaningful delivery of the drug to the lungs, which requires good adherence and a proper inhaler technique from the

patient. Up to 80% of the inhaled drug ends up impacting in the oropharynx and being systemically absorbed, even when good technique is used. Accordingly, spacer devices are suggested to improve drug delivery to the lungs⁴.

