4.2.2 Secondary objective

Comparison of database outcomes for non-extrafine beclomethasone dipropionate with Volumatic[®] spacer and non-extrafine beclomethasone dipropionate with Aerochamber[®] spacer in terms of Read codes for adverse reactions to beclomethasone dipropionate over a three-year period.

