5.4 Study design (database outcomes)

This is a historical database study composed of a 1-year baseline period for demographics, characterisation and matching. The index date is the date of prescription of a spacer (Volumatic[®] or Aerochamber[®]), with a 3-year outcome period for detection of adverse events. Patients will require 4 years' continuous practice data.

[figure not shown]

Figure 5: Study Design (database outcomes) extractions from 2005 onwards

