6.2 Inclusion and exclusion criteria (database outcomes)

Inclusion criteria

Diagnosis for asthma (confirmed by diagnostic Read code)

Age ≤65 years at index date for main outcomes, all ages for exploratory

4-years of continuous practice data comprising 1-year baseline data and 3-year outcome data

≥2 separate prescriptions of the beclomethasone pMDI in outcome year after index prescription date

Stepped down ICS in outcome period

Spacer prescription (Aerochamber or Volumatic)

Exclusion criteria

Received multiple types of ICS or FDC ICS/LABA during the baseline period, at the index date or during the outcome period

Prescribed both Aerochamber and Volumatic spacers

Table 7: Inclusion and exclusion criteria for database outcomes

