7.2 Demographics and baseline variables for database outcomes

- Gender (male/female)

* Calculated as average number of puffs per day over the year multiplied by strength (in µg);
i.e. $\frac{\text{Number of inhalers} \times \text{doses per inhaler}}{365} * \text{strength}$

† See appendix 1 for definitions

- Age of patient (years, at index date)
- Body Mass Index (BMI, at time nearest index date, calculated from height and weight data if available, otherwise taken from practice-recorded BMI value, detailed definition in Appendix 1)
- Smoking status (identified by Read code, closest to index date)
- SABA daily dose calculated in baseline prior to index date*
- Percentage predicted peak flow (peak flow predicted, closest to index date)
- Total cumulative ICS dose
- Total cumulative non-extrafine beclomethasone dipropionate therapy
- Duration of ICS therapy
- Number of exacerbations (ATS/ERS 2015 consensus definition[†]) prior to index date
- Number of oral corticosteroid prescriptions prior to index date
- Number of antibiotic prescriptions for lower respiratory tract infections prior to index date
- History of comorbidities related to asthma:
 - Pneumonia (Read code diagnosis in the year prior to the index date)
 - Diabetes (Read code diagnosis and/or antidiabetic drugs ever prior to the index date)
 - Ischaemic heart disease (Read code diagnosis prior to the index date)
 - Rhinitis (Read code diagnosis, including chronic and allergic rhinitis and prescriptions for nasal steroids prior to index date)
 - Eczema (Read code diagnosis prior to index date)
 - Osteoporosis (Read code diagnosis prior to the index date)
 - Charlson Comorbidity Index (based on Read code diagnoses in the year prior to index date, detailed definition in Appendix 1)

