7.4 Database outcomes

Total and individual database outcomes including Read code diagnosis for

- 1) Oral thrush
- 2) Rash
- 3) Oedema/swelling
- 4) Adrenal suppression diagnosis
- 5) Osteoporosis/osteopenia
- 6) Anxiety/depression
- 7) Cataracts
- 8) Glaucoma

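### The secondary database total has three inconsistent outcome lists and no new-onset rule, so chronic disease present before the spacer can count as an adverse event

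*Protocol*

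**What the plan says.** Three places in the protocol describe the database endpoint.

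- **Section 8.4.2** compares "The total number of adverse events as listed in the Summary of Product characteristics in the outcome period" by conditional Poisson regression with adjustment for baseline confounders, and states: "The adjusted rate ratio with 95% confidence interval will be reported".
- **Section 7.4** introduces "Total and individual database outcomes including Read code diagnosis for" eight items: oral thrush, rash, oedema/swelling, adrenal suppression, osteoporosis/osteopenia, anxiety/depression, cataracts and glaucoma.
- **Appendix 15.2.2** (mock tables) has seven rows. Oedema is absent, and osteoporosis appears without osteopenia.

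The surrounding text adds no restriction to new events. The secondary objective (4.2.2) is a comparison "in terms of Read codes for adverse reactions to beclomethasone dipropionate over a three-year period". Section 5.4 puts the index date at the spacer prescription, "with a 3-year outcome period for detection of adverse events". The exclusions in 6.2 are "Received multiple types of ICS or FDC ICS/LABA during the baseline period, at the index date or during the outcome period" and prescription of both spacers; an earlier diagnosis of an outcome condition is not among them. Section 7.2 records as a baseline variable "Osteoporosis (Read code diagnosis prior to the index date". Table 1 in section 3.0, the protocol's list of beclomethasone side effects, includes "Cough, bronchospasm, wheezing, dyspnoea", rated very rare.

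**The concern.** An analyst following the protocol cannot tell which codes form the secondary total. Whichever list is used, nothing says that a condition already present at index must be left out. Four of the eight diagnoses (osteoporosis/osteopenia, anxiety/depression, cataracts, glaucoma) are long-standing conditions that can pre-date the spacer and still carry a code in the following three years. A count of events also leaves open whether several codes for one condition in one patient count once or several times.

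At stake is what the secondary rate ratio means. It is meant to compare adverse reactions after a Volumatic or Aerochamber prescription. Events that the index spacer cannot have caused carry no information on that comparison, yet they enter both totals.

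**Working it through.** **1. The lists side by side.**

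| Place | What counts |
|---|---|
| 8.4.2 | everything in the product-characteristics list, as a number of events |
| Table 1 (3.0), the nearest list in the protocol | all eight conditions of 7.4, plus respiratory symptoms, headache, nausea, hoarseness, sleep disorder and others |
| 7.4 | eight diagnoses, opened by the word *including* |
| 15.2.2 | seven rows; the total is shown as n (%), which suggests patients rather than events |

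One table in 15.2.2 (under 16 years, above 1000 µg) carries the questionnaire items, cough among them. This looks like a copying slip, but it needs correcting too.

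**2. Is prior disease removed anywhere?** Sections 4.2.2, 5.4, 6.2, 7.4 and 8.4.2 contain no first-code or new-onset condition. Of the four chronic outcomes, only osteoporosis has a baseline entry in 7.2. Cataracts, glaucoma and anxiety/depression have none, and they are not among the Charlson conditions in Appendix 15.1.3. Section 8.3 selects matching variables by their relation to the primary outcome, not the database outcomes.

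**3. Are repeat codes handled?** Appendix 15.1.2 merges exacerbation events that fall within two weeks of each other. No such rule is given for the database outcomes.

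**4. Effect on the rate ratio.** The protocol gives no figure for the secondary endpoint. Its only sample-size statement (8.1) concerns the primary, and it reproduces: SE = √(0.30×0.70/293 + 0.30×0.70/147) = 0.0463; 0.13/0.0463 − 1.96 = 0.85; power 80.1% against the stated 80%. It has no bearing here.

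For 1:1 pairs with equal follow-up and no covariates, the conditional Poisson rate ratio is total Aerochamber events divided by total Volumatic events. Let s be the share of Volumatic events that are background (prevalent or unrelated), R_b the Aerochamber-to-Volumatic ratio of background events, and RR the true ratio for new events. Then

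RR_obs = s × R_b + (1 − s) × RR.

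All three inputs are assumptions.

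Balanced background (R_b = 1):

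| True RR | s = 25% | s = 50% | s = 75% | s = 90% |
|---|---|---|---|---|
| 0.67 | 0.753 | 0.835 | 0.917 | 0.967 |
| 1.50 | 1.375 | 1.25 | 1.125 | 1.05 |
| 2.00 | 1.75 | 1.50 | 1.25 | 1.10 |

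A simulation of matched pairs with between-pair variation and true RR 1.50 gave 1.245 at s = 50% and 1.124 at s = 75%.

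Unbalanced background:

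- True RR 1.0, s = 50%: R_b = 0.8 gives 0.5×0.8 + 0.5×1.0 = 0.90; R_b = 1.25 gives 1.125.
- True RR 1.5, s = 50%: R_b = 2.0 gives 0.5×2.0 + 0.5×1.5 = 1.75.
- True RR 1.5, s = 75%: R_b = 0.8 gives 0.75×0.8 + 0.25×1.5 = 0.975.

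The ratio can therefore shrink towards 1, move away from it, or cross it.

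**The case against.** The strongest reply is that code lists, first-versus-repeat rules and episode definitions are commonly left to the analysis plan, which is not shown. The product-characteristics wording in 8.4.2 may also simply name the source of the 7.4 list, since all eight items of 7.4 have a counterpart in Table 1. Osteoporosis as both baseline variable and outcome is no contradiction: recording it before index allows matching or adjustment, and 8.3 and 8.4.2 provide for both in general terms.

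Much of this stands. A reader might infer that asthma symptoms are certain to be counted. The protocol does not settle that: it follows only from the literal wording of 8.4.2 taken with Table 1. Section 7.4 names no respiratory symptom, and neither do the database rows of the mock tables. The dual listing of osteoporosis is not in itself an error, and how often chronic conditions are re-coded is not stated.

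Two things remain. The three descriptions of the endpoint disagree on the page, which is not detail deferred to another document. And the general safeguards do not reach the problem: three of the four chronic outcomes have no baseline variable, and even perfect balance would leave unrelated events in both totals.

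**Conclusion.** The point holds as a defect of endpoint definition that should be corrected. Sections 7.4 and 8.4.2 and Appendix 15.2.2 must be reconciled, and as written the total can include disease that pre-dates the spacer, possibly several times per patient.

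A reader might go further and conclude that the rate ratio is necessarily pulled towards 1, giving false reassurance about the unlicensed combination. The documents do not support that. Attenuation requires similar background rates in the two groups, which a non-randomised comparison does not assure; with unequal rates the error can go either way. Non-inferiority with a margin belongs to the primary questionnaire objective (4.2.1, 8.4.1). The secondary objective is a comparison without a decision rule. The primary analysis and its sample size are untouched.

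The size of the effect is unknown. The tabulated figures illustrate the mechanism under assumed values of s, R_b and the true ratio, and are not estimates for this study.

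**What to change.** 1. Use the eight outcomes of 7.4 as the single list in 7.4, 8.4.2 and the mock tables. Restore oedema and osteopenia to the tables, and correct the one database table that shows questionnaire items. Remove the open-ended wording in 7.4 and state that respiratory symptoms do not count.
2. For each chronic diagnosis, count only the first code after index in patients with no such code before index, at most once per patient. Derive the baseline flags from the same code lists.
3. Collapse repeat codes for acute outcomes (thrush, rash, oedema) into episodes by a stated rule, as the protocol already does for exacerbations.
4. Define the total as the sum of these incident events per patient, so that every matched pair is kept. A patient with a prior diagnosis then contributes no event for that condition, so adjust for the prior-diagnosis flags in case they differ between groups.
5. For each individual chronic outcome, analyse pairs in which both members are free of the condition at index, or match or adjust on the prior-diagnosis flag.

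The cost is a wording change and a set of baseline flags, best fixed before data extraction. The price in data is a somewhat smaller risk set and some lost pairs for each individual chronic outcome. Only one year of baseline data is guaranteed (5.4), so the flags should use all codes on record before index; some older diagnoses may still be missed.
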